### 9.2.1 General considerations

The Baseline value is defined as the last available value before the first dose of double-blind IMP. For participants randomized but not treated, the Baseline value is defined as the last available value before randomization.

Unless otherwise specified, analyses will be performed by intervention group, and overall for Baseline and demographics characteristics.

Interventions groups will be presented as follows:

- Period A (up to Week 16): SAR442970 and Placebo.
- Period B (from Week 16 to Week 28) and Period C (from Week 28 to Week 36): SAR442970/SAR442970 and Placebo/SAR442970.

The observation period will be divided into 4 segments:

- The **pretreatment** period is defined as the period up to first IMP administration.
- The **treatment-emergent (TE) period** is defined as the period from the first IMP administration to the last IMP administration + 75 days. The TE period includes the following 2 periods:
  - The **on-treatment period** is defined as the period from the first IMP administration to the last administration of the IMP + 14 days.
  - The **residual treatment period** is defined as the period from the end of the on-treatment period to the end of the TE period.
- The **post-treatment period** is defined as the period from the end of the TE period.

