2 STATISTICAL ANALYSES

2.1 GENERAL CONSIDERATIONS

In general, continuous data will be summarized using the number of observations available, mean, standard deviation (SD), median, Q1, Q3, minimum, and maximum. Categorical and ordinal data will be summarized using the count and percentage of participants.

The baseline value is defined as the last available value before the first dose of double-blind IMP. For participants randomized but not treated, the baseline value is defined as the last available value before randomization.

Unless otherwise specified, analyses will be performed by intervention group and overall, for baseline and demographics characteristics.

The intervention groups will be presented as follows:

- Period A: SAR442970 150mg q2w and Placebo.
- Period B and Period C: SAR442970 150 mg q2w/SAR442970 150 mg q2w, Placebo/SAR442970 150 mg q2w and overall unless otherwise specified.

Observation period

The observation period will be divided into the following segments:

The pre-treatment period is defined as the period up to first blinded IMP administration.

Period A:

- The **treatment-emergent (TE) period of Period A** is defined as the period from the first blinded IMP administration to the last blinded IMP administration + 75 days or the first open-label IMP administration, whichever occurs earlier. The TE period of Period A includes the following 2 sub-periods:
 - The **on-treatment period of Period A** is defined as the period from the first blinded IMP administration to the last blinded administration of the IMP + 14 days, or the first open-label IMP administration, whichever occurs earlier.
 - The **residual treatment period of Period A** is defined as the period after the end of the on-treatment period of Period A to the end of the TE period of Period A.

Period B:

- The **treatment-emergent (TE) period of Period B** is defined as the period from the first open-label IMP administration to the last open-label IMP administration + 75 days. The TE period of Period B includes the following 2 sub-periods:
 - The **on-treatment period of Period B** is defined as the period from the first open-label IMP administration to the last open-label administration of the IMP + 14 days.

- The **residual treatment period of Period B** is defined as the period after the end of the on-treatment period of Period B to the end of the TE period of Period B.

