2.7 SAFETY ANALYSES

All safety analyses will be performed for Period A and Period B separately, on the safety populations as defined in [Section 1.3](#), unless otherwise specified, using the following common rules:

- The analysis of the safety variables will be essentially descriptive, and no statistical testing is planned.
- Safety data in participants who do not belong to the safety population (e.g., exposed but not randomized) will be provided separately.

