Potentially clinically significant abnormality (PCSA) analyses will be performed based on the PCSA list currently in effect at Sanofi at the time of the database lock. For parameters for which no PCSA criteria are defined, similar analyses will be done using the normal range, if applicable. For parameters defined as efficacy endpoints, PCSA summaries will not be provided.

Analyses according to PCSA will be performed based on the worst value during the treatment-emergent period, using all measurements (either local or central, either scheduled, nonscheduled or repeated).

For laboratory variables, vital signs, and ECG variables above, the incidence of participants with at least one PCSA during the treatment-emergent period will be summarized regardless of the baseline level and according to the following baseline status categories:

- Normal/missing
- Abnormal according to PCSA criterion or criteria

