2.8.3.1 Biomarkers-specific analyses

2.8.3.1.1 Blood biomarkers

Analysis of blood biomarkers will be performed for markers associated with HS and/or SAR442970 activity, including:

- sTNF (soluble Tumor Necrosis Factor)
- sOX40L (soluble OX40 Ligand)
- Lipocalin-2
- CRP (C-Reactive Protein)
- hsCRP (High-Sensitivity C-Reactive Protein)
- SAA (Serum Amyloid A)
- ASCA (Anti-Saccharomyces cerevisiae antibodies)
- ACPA (Anti-Citrullinated Protein Antibodies)
- Absolute neutrophil count
- ESR (Erythrocyte Sedimentation Rate)
- IL-6 (Interleukin-6)
- CXCL13 (C-X-C Motif Chemokine Ligand 13)
- YKL40

For all the blood biomarkers,

- descriptive statistics at baseline and under treatment (table),
- boxplots and/or time profile plots (means \pm SEM)

will be reported by the study intervention group at each visit in both Periods A and B. Both the raw analysis values, change and percent change from baseline will be reported. Data will be log-transformed as appropriate.

Additionally, for period B, fold change, percent change, and absolute change from Week 16 to Week 28 will be calculated for all biomarkers mentioned above. These analyses will compare participants from period A and B. Also, for sTNF and sOX40L, fold change, percent change, and absolute change from Week 16 to Week 36 will also be presented for both groups of participants.

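### Period B laboratory and vital-sign tables for the Placebo/SAR442970 group use only a pre-placebo baseline, so the PCSA split by baseline status and the changes from baseline mix time on placebo with time on drug

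*SAP*

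**What the plan says.** SAP 2.1 gives one baseline for laboratory, vital-sign and ECG variables: "The baseline value is defined as the last available value before the first dose of double-blind IMP". Protocol 9.2.1 has the same definition. No separate baseline is defined for Period B. SAP Table 12 restarts Day 1 at the first open-label dose, but its Period B rows begin at Week 18 and include no baseline row.

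SAP 2.7 states: "All safety analyses will be performed for Period A and Period B separately". The treatment-emergent period of Period B "is defined as the period from the first open-label IMP administration to the last open-label IMP administration + 75 days" (SAP 2.1). Period B results are shown for SAR442970/SAR442970, Placebo/SAR442970 and overall.

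On counting, SAP 2.7.3.1 says: "Analyses according to PCSA will be performed based on the worst value during the treatment-emergent period, using all measurements". It adds that "the incidence of participants with at least one PCSA during the treatment-emergent period will be summarized regardless of the baseline level", and also by two baseline status categories, namely Normal/missing and Abnormal. The same section plans by-window summaries of results and of changes from baseline.

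**The concern.** The treatment-emergent clock restarts at the first open-label dose, but the baseline does not. For participants who stay on SAR442970 throughout, a pre-treatment reference is sensible. For placebo participants who switch, it is a value taken before eight placebo doses.

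The PCSA rule does not require the abnormality to start or worsen within the period. The adverse-event rule in SAP 2.7.2 does: an event must have developed, worsened or become serious in the treatment-emergent period. For blood biomarkers the SAP does use a Week 16 reference: "fold change, percent change, and absolute change from Week 16 to Week 28 will be calculated for all biomarkers mentioned above" (SAP 2.8.3.1.1).

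PCSA incidence in laboratory tests and vital signs is a listed secondary endpoint. The switchers supply the only first-exposure data in Period B, and each should have a value taken just before first exposure. The planned baseline split and change tables do not use that value as a reference. In a column of at most 28, one participant is 1/28 = 3.6 percentage points.

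**Working it through.** **Tracing the rule.** The plan states no figure on this point, so the check starts from its definitions. Take three placebo participants who enter Period B.

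- Normal at Week 0, abnormal on placebo, still abnormal at a Period B measurement. The worst Period B value meets the criterion and baseline is normal, so the participant is counted under Normal/missing in a SAR442970 column.
- Abnormal at Week 0, normal by Week 16, abnormal again on SAR442970. The participant is counted under Abnormal, so a recurrence on drug looks pre-existing.
- Abnormal on placebo and resolved before the first open-label dose, with no later abnormality. The participant is not counted in Period B, and there is no problem.

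**Change from baseline.** At Week 20 the tabulated change is (Week 20 - Week 0) = (Week 16 - Week 0) + (Week 20 - Week 16). For switchers the first term is entirely on placebo.

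**Number affected.** From SAP 1.1, 84 participants are randomized 2:1, so 84/3 = 28 are on placebo (66/3 = 22 naïve and 18/3 = 6 TNF-experienced). This is a ceiling, because the Period B safety population requires an open-label dose.

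**Scale of the first case.** Let a be the onset of a given PCSA on placebo, s the share still abnormal at a Period B measurement, and b the true new onset in Period B. None of these is in the documents; all are assumptions. Assume also that all 28 are normal at Week 0 and all enter Period B.

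- Carried-in proportion = a × s
- Reported proportion in the Normal/missing row = a × s + (1 - a × s) × b

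| a | s | b | Carried in | Of 28 | Reported | Of 28 |
|---|---|---|---|---|---|---|
| 5% | 0% | 5% | 0.0% | 0.0 | 5.0% | 1.4 |
| 5% | 50% | 5% | 2.5% | 0.7 | 7.4% | 2.1 |
| 10% | 50% | 5% | 5.0% | 1.4 | 9.8% | 2.7 |
| 20% | 100% | 5% | 20.0% | 5.6 | 24.0% | 6.7 |

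Worked line: with a = 10% and s = 50%, a × s = 0.05, and 0.05 + 0.95 × 0.05 = 0.0975, which is 2.7 of 28. With the last value before the first open-label dose as reference, the 1.4 carried-in cases leave the normal-at-reference row. The reverse case (recurrence on drug) is not quantified.

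**Is a better reference available?** For laboratory and vital-sign variables it is. Both flowcharts in Protocol 1.3 schedule vital signs, non-fasting laboratory tests and the fasting lipid panel at Week 16, and the prescribed order of assessments puts vital signs and blood sampling before dosing. For ECG, the flowcharts as extracted show Screening, Week 18, EOT and EOS, with none at Week 16. Column placement may be a conversion artefact. If it is correct, the last ECG before the first open-label dose would usually be the Screening one, and nothing changes.

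**The case against.** The strongest opposing case has five parts.

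- **The SAP never calls these abnormalities new or drug-caused.** A reader might infer that it reports placebo-onset abnormalities as newly emergent on SAR442970. It does not say so, and the row regardless of baseline counts pre-existing abnormalities by design. This stands. The problem is confined to the baseline split, where the Normal/missing row invites that reading, and to the change tables.
- **Change on drug is partly visible.** Absolute neutrophil count is on the biomarker list, so it already has a planned Week 16 to Week 28 change. By-window results, with a Week 16 window closing at the first open-label dose, let a reader compare means before and after the switch. This also stands, so it would be wrong to say that the change on drug is not shown. Platelets, ALT, lipids, creatinine and vital signs still have no paired change from Week 16.
- **Marked cases may not reach Period B.** Protocol 7.1.1 lists low neutrophils, low platelets and raised ALT among the reasons for permanent discontinuation. Where another cause is evident, IMP may resume only after sufficient normalization. Many of the more severe carried-in cases would therefore be absent, which weakens any argument built on cytopenia. Milder PCSAs and other parameters remain.
- **Other displays help.** Switchers have their own column, Period A is tabulated separately, and clinically significant abnormalities are also adverse events under a rule that requires onset or worsening. Aggregate tables still cannot show which Period B cases were carried in, and the overall column absorbs them.
- **Replacing the baseline in one group has a cost.** It would mix references in the overall column and depart from the protocol definition. This stands, and it is why the fix adds a reference and keeps the Week 0 one.

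**Conclusion.** The point holds in limited form. For Placebo/SAR442970 participants in Period B, the PCSA split by baseline status and the changes from baseline in laboratory and vital-sign variables rest on a pre-placebo value. Placebo-onset abnormalities that persist fall in the Normal/missing row of a SAR442970 column, and recurrences on drug can fall in the Abnormal row. The row regardless of baseline, the SAR442970/SAR442970 group and the planned Week 16 to Week 28 neutrophil change are not affected. ECG gains little under the schedule as extracted.

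The size is unknown. Under assumed onset of 5-20% and persistence of 0-100%, carried-in cases number 0 to 5.6 of 28 for a given PCSA, or 0 to 20 percentage points. The upper end needs 20% onset with every case persisting. It also needs all 28 participants to be normal at Week 0 and to enter Period B, and the discontinuation criteria make that less likely for marked cytopenia or ALT rises. The documents do not support a claim that a particular number of false drug-emergent abnormalities will be reported.

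**What to change.** In SAP 2.1 and 2.7.3.1, for the Placebo/SAR442970 group in Period B:

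- Add the last value before the first open-label dose as the reference for PCSA baseline status and for change from baseline in laboratory and vital-sign variables. Apply it to ECG only where such a value exists.
- Keep the Week 0 reference as a labelled supplementary display.
- In the overall column, use only the Week 0 reference, or footnote that references are mixed.

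The SAR442970/SAR442970 group keeps its Week 0 baseline. The cost is one derived variable and some additional labelled tables. The Week 16 laboratory and vital-sign values are already scheduled, so no new assessment is needed and no clinical rule changes.

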2.8 OTHER ANALYSES

2.8.1 PK analyses

SAR442970 concentrations at selected time points will be reported using the following descriptive statistics: mean, geometric mean, median, standard deviation, coefficient of variation, minimum and maximum. All concentration values LLOQ/2 will be treated as zero in all summary statistics excepted for the geometric mean and associated coefficient of variation for which they will be considered as missing. A listing of PK concentration will be provided, using “<LLOQ/2” for values below LLOQ/2.

PK parameters such as C_{max} , t_{max} , $t_{1/2z}$, and AUC_{0-tau} will be estimated using a population PK approach. These parameters will be presented in a separate standalone report provided under the responsibility of Sanofi TMED PKDM Department.

2.8.2 Immunogenicity analyses

Antidrug antibodies were assessed at baseline (before first IMP administration), Week 2, Week 4, Week 16, Week 28/EOT or premature and at EOS (Week 36 or 8 weeks after premature EOT).

A 3-tiered approach will be employed to generate titer data. Serum samples will be screened for antibodies binding to SAR442970 and the titer of confirmed positive samples will be reported as a quantitative variable.

Incidence will be provided for the following ADA response categories:

- Participants with **pre-existing ADAs** correspond to participants with ADAs present in samples drawn before first administration of intervention. Participants with missing ADA sample at baseline will be considered as without pre-existing ADA.
- Participants with **treatment-emergent ADA** correspond to participants with at least one treatment-induced/boosted ADA.
 - Participants with **treatment-induced ADAs** correspond to participants with ADAs that developed at any time after first IMP administration and without pre-existing ADA (including participants without pre-treatment samples).
 - Participants with **treatment-boosted ADAs** correspond to participants with pre-existing ADAs that are boosted at any time after first IMP administration to a significant higher titer than the baseline. A 3-fold serial dilution schema is used during titration, so at least a 9-fold increase will be considered as significant.
- Participants with **unclassified ADA** correspond to participants with pre-existing ADAs that cannot be classified as treatment-boosted ADA because of missing titer(s) (i.e., a positive ADA sample at any time after first IMP administration in a participant with pre-existing ADA but with missing titer at this sample or at baseline).
- Participants **without treatment-emergent ADA** correspond to participants without treatment-induced/boosted ADA and without any inconclusive sample nor unclassified ADA at any time after first IMP administration.

- Participants **with inconclusive ADA** are defined as participants which cannot irrefutably be classified as with or without treatment-emergent ADA.

Summary of ADA at baseline, listing of participants with treatment-emergent ADA and summary table of incidence will be provided for each SAR442970 related ADA variables on the ADA population. A summary of ADA at baseline and at each visit during the treatment-emergent period (including follow-up) might be provided depending on ADA incidence.

Additional analysis may be performed to further characterize the immunogenicity of SAR442970.

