*bb* Hidradenitis Suppurativa Clinical Parameters will be performed at each designated study visit and must address all relevant anatomical regions in each participant; the number, location, longest distance between relevant lesions, and whether the lesions are separated by normal-appearing skin will be measured in each anatomical area ; Hurley Stage is included as an assessment performed during the HS clinical parameters; Hidradenitis Suppurativa Physician's Global Assessment is included as an assessment performed during the HS clinical parameters. The site is responsible for counting lesions that received intervention as permanently present in the lesion counts from the date of the intervention. The data collected from the HS clinical parameters will be used for the derivation of the HiSCR50, HiSCR75, HiSCR90, IHS4, AN count, Hidradenitis Suppurative Physician's Global Assessment, raw counts, and disease flares. For each participant it is recommended that the HS Clinical Parameters is assessed by the same Investigator during the entire study if possible.

*cc* Investigator review of participant daily analgesic use diary.

*dd* The participant should complete the questionnaire before site personnel perform any clinic assessments and before any interaction with the site personnel has occurred to avoid biasing the participant's response.

*ee* Number of samples (tubes) and quantity of biological samples needed for each assessment can be found in the laboratory manual.

*ff* Up to 4 hours prior to IMP administration.

*gg* PD biomarkers will include serum TNF and serum OX40L.

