Hidradenitis suppurativa is a chronic disease and an additional goal of therapy aside after achievement of initial efficacy is sustained efficacy. Patients on adalimumab, the only approved biologic therapy for HS, have been shown to lose clinical response in a couple of years when they may require long-term treatment for this chronic disease. However, a placebo-controlled study greater than 16 weeks is not possible in HS participants due to concerns of withholding active treatment from placebo participants for longer than 16 weeks. Thus, a 12-week open-label period was included to obtain an indirect understanding of the efficacy and safety of SAR442970 after 28 weeks of administration. Participants randomized to SAR442970 at Baseline will continue to receive SAR442970 from Week 16 to Week 26 to complete 28 weeks of treatment with SAR442970 in total. Participants randomized to placebo at Baseline will begin to receive SAR442970 at the Week 16 visit and will continue until Week 26 to complete 16 weeks of treatment with placebo and 12 weeks of treatment with SAR442970 in total. An 8-week post-treatment Follow-up Period was included to assess for safety outcomes. For participants in the US, response will be assessed at the Week 20 visit (see definition of response in [Section 4.1](#)). Responders at Week 20 will continue in Period B to complete the 12-week open-label period. Non-responders at Week 20 will move directly to the safety follow-up period so that they may complete the study and receive access to other treatments for their disease per Investigator discretion.

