**Table 5 - Study intervention(s) administered**

|  |   |   |
|--|---|---|
| Intervention label                  | SAR442970   | SAR442970 matching placebo  |
| Intervention name                   | SAR442970   | Placebo   |
| Type                                | Drug  | Other   |
| Dose formulation                    | 1 mL extractable volume of 150 mg/mL
SAR442970 filled in 2 mL glass vial                           | 1 mL extractable volume of placebo filled
in 2 mL glass vial                                       |
| Unit dose strength(s)               | 150 mg  | 0 mg  |
| Dosage level(s)                     | 150 mg every 2 weeks  | 0 mg every 2 weeks  |
| Route of administration             | Subcutaneous injection  | Subcutaneous injection  |
| Use                                 | Experimental  | Experimental  |
| IMP                                 | IMP   | IMP   |
| Packaging and labeling              | One vial in a kit box. Both the box and the vial will be labeled as required per country requirement. | One vial in a kit box. Both the box and the vial will be labeled as required per country requirement. |
| Current/former name(s) or alias(es) | NANOBODY® VHH anti-TNF $\alpha$ /OX40L  | Not applicable  |

Abbreviations: IMP=investigational medicinal product

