Safety of Period B	All randomized participants who continue in Period B and who have taken at least one dose of study intervention of Period B, regardless of the amount of intervention administered. Participants will be analyzed according to the intervention they actually received.
Pharmacokinetics (PK) of Period B	All participants from the safety population of Period B with at least one post-Baseline PK result. Participants will be analyzed according to the intervention they actually received.
Biomarker PD of Period B	All participants from the safety population of Period B with biomarker results available at baseline and at least one post-baseline visit.

		Participants will be analyzed according to the intervention they actually received. Randomized participants for whom it is unclear whether they took the study medication will be included.
	Biomarker predictive of Period B	All participants from the safety population of Period B with a baseline biomarker result. Participants will be analyzed according to the intervention they actually received. Randomized participants for whom it is unclear whether they took the study medication will be included.
Period A and Period B	Antidrug antibody (ADA)	All participants from the safety population treated with SAR442970 with at least one post-Baseline ADA result (positive, negative, or inconclusive). Participants will be analyzed according to the intervention they actually received.

Abbreviations: ADA=anti-drug antibody; ICF=informed consent form; IRT= interactive response technology; PK=pharmacokinetic(s); PD=Pharmacodynamic(s); TNF=tumor necrosis factor.

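### For placebo participants who switch at Week 16, treatment-emergent ADA is counted from the first placebo injection rather than from the first SAR442970 dose

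*SAP*

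**What the plan says.** SAP 2.8.2 sets out the ADA categories. Induced antibodies are "ADAs that developed at any time after first IMP administration and without pre-existing ADA". Boosted antibodies are "pre-existing ADAs that are boosted at any time after first IMP administration to a significant higher titer than the baseline", where a rise of at least 9-fold is needed. A missing baseline is handled by the rule "Participants with missing ADA sample at baseline will be considered as without pre-existing ADA". The sampling times are given as: "Antidrug antibodies were assessed at baseline (before first IMP administration), Week 2, Week 4, Week 16, Week 28/EOT or premature and at EOS".

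SAP 1.3 (Table 4) has one ADA population across Periods A and B: "All participants from the safety population treated with SAR442970 with at least one post-Baseline ADA result". SAP 2.1 takes baseline as the last value before the first double-blind dose and defines no second baseline for participants who switch.

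Protocol Table 5 has a column for "SAR442970 matching placebo" and marks it as IMP, just as it marks SAR442970. Protocol 4.2 states: "Participants randomized to placebo at Baseline will begin to receive SAR442970 at the Week 16 visit". The schedule of activities (Protocol 1.3.1) times ADA sampling as "Up to 4 hours prior to IMP administration", so the Week 16 sample comes before the first open-label dose.

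**The concern.** An antibody category meant to describe the response to SAR442970 should start from exposure to SAR442970. For the Placebo/SAR442970 sequence it starts 16 weeks too early. There are two consequences.

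- **Numerator.** A positive result while the participant has received only placebo, whether from assay background or from some other reactivity, is classed as treatment-emergent.
- **Denominator.** Entry to the ADA population needs only treatment with SAR442970 and one result after baseline. A switcher who takes SAR442970 and then leaves without another ADA sample enters on placebo-phase results. If those are negative, the participant is reported as having no treatment-emergent ADA, although no sample was taken after drug.

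ADA incidence is a named secondary endpoint, and Protocol 3.1 says antibodies may affect efficacy or safety. The switchers also show what 12 weeks of exposure does, so their pre-drug baseline matters. The SAP does restart the clock elsewhere: SAP 2.1 defines a Period B treatment-emergent period from the first open-label dose, and the analysis windows in SAP Appendix 4 reset Day 1 for Period B. The ADA definitions have no counterpart.

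**Working it through.** The plan states no figure on this point, so there is nothing to reproduce. The check traces the rule through the schedule and then sizes it under stated assumptions.

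**Step 1: which samples can trigger the label.** The post-baseline ADA samples are Weeks 2, 4, 16, 28/EOT and EOS, five in all. For a switcher the first SAR442970 dose is at Week 16, after that visit's sample. Samples before any SAR442970: Weeks 2, 4 and 16, which is 3 of 5 = 60%. As the SAP is written all five can make the participant treatment-emergent. With the starting point at the first SAR442970 dose, only the last two can.

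**Step 2: how many participants.** 84 randomized 2:1 gives 84/3 = 28 on placebo. The secondary ADA objective is stated for the naïve subgroup: 66/3 = 22.

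**Step 3: gross count.** Let f be the chance that a drug-free sample is called positive. The documents do not give f, so 1%, 3% and 5% are assumptions. Assume also independent samples, all three assayed, no pre-existing ADA, and every placebo participant switching. The chance of at least one positive is 1 − (1 − f)³.

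| f | 1 − (1 − f)³ | × 28 | × 22 |
|---|---|---|---|
| 1% | 0.0297 | 0.83 | 0.65 |
| 3% | 0.0873 | 2.45 | 1.92 |
| 5% | 0.1426 | 3.99 | 3.14 |

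**Step 4: net count.** A participant who later becomes positive on drug is treatment-emergent in any case. Protocol 2.2.1.2.1 reports 57.1% in the 150 mg repeat-dose cohort of healthy volunteers. If that rate carries over and is independent of the pre-drug result, the net count is the gross count × (1 − 0.571) = gross × 0.429.

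| f | net of 28 | net of 22 |
|---|---|---|
| 1% | 0.36 | 0.28 |
| 3% | 1.05 | 0.82 |
| 5% | 1.71 | 1.35 |

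On the incidence scale, a true 57.1% in switchers would be reported as 57.1 + 42.9 × 0.0297 = 58.4% at f = 1%, and as 57.1 + 42.9 × 0.1426 = 63.2% at f = 5%.

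**Step 5: the opposite error.** The number of switchers who start SAR442970 and give no later ADA sample cannot be derived from the documents, so it is not sized.

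**The case against.** The strongest reply is that the placebo-phase samples may never be assayed. Protocol 6.4 lets the laboratory sort samples by arm and begin with the SAR442970 group while the study is running. If the placebo-phase samples stay untested, none can be positive and the counts above are zero. That is possible, but it is a laboratory step and not an analysis rule, and Protocol 8.9 says antibodies are evaluated in samples from all participants. The documents leave the matter open. Leaving the placebo arm's baseline untested would not make the classification sound either: the missing-baseline rule would then treat reactivity that predates the drug, found at Week 28 or EOS, as induced. That rule applies to every arm and is not itself a crossover defect.

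A second reply is that IMP might mean SAR442970 only. A footnote to the schedule of activities does set IMP and placebo side by side as alternatives. Table 5, and the SAP's use of blinded IMP for both arms, point the other way.

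The sizing is also open to fair criticism. Only confirmed positives count. Persistent background reactivity would probably show at baseline too, and such a participant is then pre-existing and needs a 9-fold rise. Both lower the count.

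Three stronger readings are tempting. A reader might infer that up to 4 of 28 participants will be wrongly reported. That is a gross figure on assumed rates, and it ignores those who turn positive on drug. A reader might infer that the plan cannot show switchers separately. SAP 2.1 already makes presentation by sequence the default for Periods B and C, and 2.8.2 does not override it. A reader might also infer that efficacy conclusions are at risk. None depends on these categories.

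**Conclusion.** The definitional point stands and does not depend on any assumed rate: as written, samples taken before any SAR442970 can make a switcher treatment-emergent, and a switcher with no sample after drug can be counted as negative. No section of either document gives these participants a new baseline.

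The effect is small and uncertain. Under the assumptions in the working it is about 0.8 to 4.0 of 28 gross (0.7 to 3.1 of 22 naïve) and about 0.4 to 1.7 of 28 net (0.3 to 1.3 of 22). It is zero through this route if placebo-phase samples are not assayed. The endpoint is descriptive. The change is still worth making before database lock, because it concerns a stated rule on a secondary endpoint and is cheap to correct.

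**What to change.** Add to SAP 2.8.2: for Placebo/SAR442970 participants, pre-existing, treatment-induced and treatment-boosted ADA are defined relative to the first SAR442970 administration, with the last sample before that dose (normally Week 16 pre-dose) as baseline. Amend the ADA population in SAP Table 4 to require at least one ADA result after the first SAR442970 dose.

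The schedule already collects the samples, so no visit or procedure changes. Two costs remain. The placebo arm's pre-dose Week 16 samples must be assayed. Protocol 8.9 implies this already, but the sorting step in Protocol 6.4 leaves it open while the study is ongoing, so the laboratory instruction should be confirmed. Also, a false positive at Week 16 would class the participant as pre-existing and so require a 9-fold rise. At the assumed 1% to 5% that is 28 × 0.01 = 0.3 to 28 × 0.05 = 1.4 participants. The SAR442970 arm carries the same risk at its Week 0 baseline, so the two sequences would be treated alike.
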